2.6. Evaluation items

The primary endpoint of this clinical trial is the disease control rate of non-irradiated target lesions, in order to explore the efficacy (additive effect) of radiotherapy to immunotherapy with nivolumab, which is already established as third-line chemotherapy in unresectable advanced or recurrent gastric cancer. Secondary endpoints will also include 1) median survival time (MST) and 2) safety (grade and frequency of adverse events), 3) local control rate (disease control rate of irradiated target lesions), and 4) immunological parameters.

(1) Primary endpoint

Disease control rate

The rate of patients with a best overall response of stable disease (SD) or better confirmed by 180 days, starting from the start date of radiotherapy (Day 1). CT (MRI is also acceptable) and whole-body PET-CT will be used to determine overall response such as complete response (CR), partial response (PR), SD, progressive disease (PD) at each imaging time according to the RECIST Guidelines Version 1.1. If imaging is not available, the patient is considered deficient (NE). CR or PR as the best overall response is defined as two or more consecutive CRs or PRs. If the best overall response does not meet the criteria for CR or PR, and the patient has no PD on the 6th dose of nivolumab and Day 120, the best overall response is considered to be SD. For evaluation, target lesions other than those treated with local radiotherapy are considered as target lesions. If the lesions cannot be evaluated based on the above criteria, they will not be included in the analysis for best overall response.

(2) Secondary endpoint

1) Median survival time (MST)

Overall survival is defined as the period from the start date of radiotherapy until the date of death from any cause. In surviving cases, the last date of confirmation of survival is the date of termination (survival confirmed by telephone contact is acceptable, but confirmation of survival should be recorded in the medical record). Untraceable cases are terminated on the last date of confirmed survival before the loss of follow-up. At the end of the study period, all enrolled cases will be confirmed alive.

2) Safety (grade and frequency of adverse events)

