 - * According to advance of immunological technique, the contents of immunological parameter analyses, such as antigen-specific T cell function analysis, highly multiplexed flow cytometric analysis, T cell receptor repertoire analysis, and assessment of tumor mutation burden using plasma derived ctDNA, will also be evaluated.
 - * These analysis will be performed relating to clinical outcomes, such as two groups divided with MST.

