- 5) Blood biochemistry: total protein, albumin, total bilirubin, direct bilirubin, AST, ALT, ALP, γ -GTP, BUN, creatinine, LDH, uric acid, CPK, P, Ca, Na, K, Cl, CRP, blood glucose.
- 6) Presence of adverse events (CTCAE v4.0 Japanese translation).
- 7) Immunological parameters.

During nivolumab administration

(After the second dose, assess the following items on the day of administration or the day before administration. Assess following items once from 7 days before to 7 days after the imaging examination date.)

- 1) General findings (temperature, blood pressure, pulse).
- 2) General condition: PS (ECOG).
- 3) Subjective and objective symptoms: fever, nausea, vomiting, diarrhea, decreased appetite, etc. (to be confirmed according to CTCAE v4.0 Japanese translation).
- 4) Blood count (peripheral blood): white blood cell count and fractions, red blood cell count, hemoglobin, MCV, MCH, MCHC, Ht, platelets.
- 5) Blood biochemistry: total protein, albumin, total bilirubin, direct bilirubin, AST, ALT, ALP, γ -GTP, BUN, creatinine, LDH, uric acid, CPK, P, Ca, Na, K, Cl, CRP, blood sugar.
(The following items are only available at the third and sixth doses) RA, ANA, SP-D, KL-6, TSH, free T3, free T4, tumor markers (CEA, CA19-9).
- 6) Contrast-enhanced CT of the chest, abdomen and pelvis (at third and sixth doses). PET-CT is also acceptable. Add MRI if necessary.
- 7) Presence or absence of PD (diagnosed comprehensively based on imaging and clinical findings).
- 8) Presence or absence of adverse events (CTCAE v4.0 Japanese translation).
- 9) Immunological parameters.

During observation

(Assess following items once from 14 days before to 14 days after the 3rd and 6th dose of Nivolumab and Day120.)

- 1) Contrast-enhanced CT of chest, abdomen and pelvis. PET-CT is also acceptable. Add MRI if necessary.

After completion of the protocol

(Assess following items once from 14 days before to 14 days after the Day180.)

- 1) General findings (temperature, blood pressure, pulse).
- 2) General condition: PS (ECOG).
- 3) Subjective and objective symptoms: fever, nausea, vomiting, diarrhea, decreased appetite, etc. (to be confirmed according to CTCAE v4.0 Japanese translation).
- 4) Blood count (peripheral blood): white blood cell count and fractions, red blood cell count, hemoglobin, MCV, MCH, MCHC, Ht, platelets.

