2.8. Expected number of cases

40 cases.

Basis for setting

Based on a previous study (ONO-4538-12 study) (5), the disease control rate is set at 40%. At a one-side significance level of 5% and a power of 80%, a sample size of 39 cases are required to detect an additional 20% improvement expected from the study treatment.

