2.11. During the study

Registration period: March 1, 2018 to August 31, 2020

Total study period: March 1, 2018 to August 31. 2021

3. Policy for selecting research subjects

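### The only outcome analysis named for the immunological markers is an example, a split at median survival time; a Cox model would use more of the survival data, and late samples need a landmark or time-dependent analysis

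*Protocol*

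**What the plan says.** Protocol 1.2 and 2.6 list immunological parameters as the fourth secondary endpoint. Protocol 1.1 presents the trial as a proof of concept that includes exploratory immunological analyses. After listing the assays, Protocol 2.6 adds: "These analysis will be performed relating to clinical outcomes, such as two groups divided with MST". MST is the median survival time.

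No other method is given. Under immunological parameters, Protocol 2.10 says only where the assays will be run. The SAP covers disease control, survival, local control and safety, with no section on immunological parameters. SAP 6.7 plans survival subgroups by treatment completion and irradiation site, and names no marker.

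Protocol 2.7 schedules immunological samples before registration, after radiotherapy, during nivolumab, at treatment cessation, and at the visit after protocol completion, whose timing rule is "Assess following items once from 14 days before to 14 days after the Day180".

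**The concern.** Dividing patients at the MST turns each survival time into a yes/no. A death at one month counts the same as a death just before the median, and a survivor of 7 months counts the same as one of 30. In a trial of 40 patients this can hide real associations of modest size.

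Late samples raise a second problem. A Day 180 value exists only in patients alive at about Day 180. A long-versus-short comparison of that value sets long survivors against the part of the short-survival group that lived long enough to be sampled, and the groups are defined by survival after the sample was taken. The immunological part of the proof of concept would rest on comparisons that are weak for early samples and hard to interpret for late ones.

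**Working it through.** **The plan's own figure.** Protocol 2.8 states: "At a one-side significance level of 5% and a power of 80%, a sample size of 39 cases are required". The target rate is 60%, which is 20 points above the reference rate of 40%. With the arcsine formula, h = 2·asin(√0.6) − 2·asin(√0.4) = 0.403, and n = ((1.645 + 0.842)/0.403)² = 38.1, so 39. The figure is reproduced, but it concerns disease control only. The documents give no effect size, test level or power for the markers.

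**Inputs from the documents.**
- n = 40 (Protocol 2.8).
- Survival: "Overall survival is defined as the period from the start date of radiotherapy until the date of death from any cause" (Protocol 2.6).
- Censoring: "In surviving cases, the last date of confirmation of survival is the date of termination" (Protocol 2.6).
- "Registration period: March 1, 2018 to August 31, 2020", with the study ending on August 31, 2021 (Protocol 2.11), gives 12 to 42 months of potential follow-up.
- Two-sided 95% intervals by default (SAP 2.2), taken here as a two-sided 5% test.

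**Assumptions.** Exponential survival; median 6 to 13 months (the background range in Protocol 1.1, which is not specific to third-line patients); uniform accrual; no loss to follow-up; a normally distributed marker acting log-linearly on the hazard; hazard ratios per SD from 1.3 to 2.5.

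**Information kept.** For survival beyond time m, S = exp(−e^η). Information per patient about η is (dS/dη)²/[S(1−S)]. At the median, e^η = ln 2 and S = 0.5, so this is (0.5·ln 2)²/0.25 = (ln 2)² = 0.48. Cox information per patient is about the fraction of patients who die:
- Median 6 months: 1 − (6/(30·ln 2))·(2^(−2) − 2^(−7)) = 0.93.
- Median 13 months: 1 − (13/(30·ln 2))·(2^(−12/13) − 2^(−42/13)) = 0.74.

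The split therefore keeps 0.48/0.93 = 52% to 0.48/0.74 = 65% of the Cox information, as if about 21 to 26 of the 40 patients were analysed.

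**Power.** Simulation with 4,000 trials per setting: Cox likelihood-ratio test against a t-test of the marker between patients dying by, and surviving beyond, the Kaplan-Meier median.

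| HR per SD | Median 6 mo: Cox / split | Relative loss | Median 13 mo: Cox / split | Relative loss |
|---|---|---|---|---|
| 1.3 | 0.34 / 0.19 | 44% | 0.28 / 0.19 | 31% |
| 1.5 | 0.62 / 0.38 | 39% | 0.54 / 0.36 | 34% |
| 1.6 | 0.73 / 0.47 | 36% | 0.65 / 0.47 | 28% |
| 1.8 | 0.87 / 0.65 | 26% | 0.83 / 0.64 | 22% |
| 2.0 | 0.96 / 0.77 | 19% | 0.93 / 0.77 | 17% |
| 2.5 | 0.995 / 0.92 | 7% | 0.99 / 0.93 | 6% |

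With no effect, both methods rejected in about 5% of trials. A separate simulation gave 22 to 28% at 1.8 and 17 to 18% at 2.0. With a Mann-Whitney test in place of the t-test, the loss is about 1 to 5 points larger.

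**Day 180 samples.** 180 days is 5.91 months.
- Median 6 months: 1 − 2^(−5.91/6) = 49.5% dead before Day 180, about 20 of 40, or nearly all of the 20 short survivors.
- Median 13 months: 1 − 2^(−5.91/13) = 27%, about 11 of 40, which leaves about 9 of the 20 short survivors.

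**The case against.** The strongest reply is that the split is only an example. Protocol 2.6 speaks of clinical outcomes in general, names no test, and does not exclude modelling survival. A reader might infer that the split is the planned and sole analysis; the text does not say so. What stands is that no other analysis is named for this endpoint in either document.

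Three stronger readings also fail:
- A reader might take the power loss to be a third or more in general. The table shows that it reaches this only for modest effects, and the largest absolute loss with the t-test is about 26 percentage points.
- A reader might expect censoring to leave patients who cannot be placed on either side of the median. With at least 12 months of potential follow-up, and survival status to be confirmed at the end of the study, this affects none of 40 at a 6-month median and about 1 of 40 at 13 months.
- A reader might call the short-survival group at Day 180 largely empty. That fits the 6-month end of the range but not the 13-month end.

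Two further points stand as limits. The simulated data follow the model that Cox fits, which favours Cox. The missing late samples are caused by early death, not by the split: a Day 180 landmark analysis loses the same patients, so the power figures for 40 patients do not carry over to late samples. The cessation-of-treatment sample does not fill the gap, because it belongs to a different time point.

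Finally, the analyses are exploratory, and neither the primary conclusion nor the sample size depends on them.

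**Conclusion.** The point holds for an exploratory secondary endpoint. The one outcome analysis named, an example, is inefficient for markers measured in everyone: it keeps about 52 to 65% of the Cox information. The relative power loss is about 30 to 45% at a hazard ratio of 1.3 to 1.5 per SD, 22 to 28% at 1.8 and under 20% at 2.0.

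These sizes rest on the assumptions listed, none of which the documents fix for markers. By the large-sample formula at a hazard ratio of 1.5, a two-sided 1% test raises the loss to 41 to 53%, and a one-sided 5% test lowers it to 23 to 30%. Tissue markers may cover fewer than 40 patients, because Protocol 2.6 limits immunohistochemistry to cases with available specimens.

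For Day 180 values the problem is interpretation. Over the assumed range of medians, at least about half of the short-survival group has no sample, and the rest are selected for having survived to the visit.

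**What to change.** In Protocol 2.6 and a short new SAP section:

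- Make the main exploratory analysis a Cox model of overall survival on each marker as a continuous variable, log-transformed where skewed, reported as a hazard ratio per SD with its 95% interval. Use the pre-registration sample and count survival from Day 1.
- For on-treatment and Day 180 values, use a landmark at the sampling time or a time-dependent covariate. This gives a valid comparison but does not recover patients who died earlier. At Day 180 about 20 (6-month median) to 29 (13-month median) of 40 would still be alive.
- Keep the MST split as a descriptive display.
- Label the results exploratory, since many markers are tested.

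The cost is SAP wording, a little more programming and a proportional-hazards assumption to check. Survival dates and samples are already collected, so no new data are needed.

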2.7. Observation and examination items

Pre-registration evaluation items (assess following items once within 14 days prior to date of registration)

- 1) Patient background (subject identification number, date of obtaining written consent, gender, age, date of birth, height, weight, presence of allergies, medical history, presence of complications, concomitant medications, drinking history, smoking history, history of treatment for cancer).
- 2) General findings (temperature, blood pressure, pulse).
- 3) General condition: PS (ECOG).

- 4) Subjective and objective symptoms: fever, nausea, vomiting, diarrhea, decreased appetite, etc. (to be confirmed according to CTCAE v4.0 Japanese translation).
- 5) Contrast-enhanced CT (or PET-CT) of chest, abdomen and pelvis, and plus contrast-enhanced MRI if necessary.
- 6) Blood count (peripheral blood): white blood cell count and fractions, red blood cell count, hemoglobin, MCV, MCH, MCHC, Ht, platelets.
- 7) Blood biochemistry: total protein, albumin, total bilirubin, direct bilirubin, AST, ALT, ALP, γ -GTP, BUN, creatinine, LDH, uric acid, CPK, P, Ca, Na, K, Cl, CRP, blood sugar, rheumatoid factor (RA), antinuclear antibodies (ANA), SP-D, KL-6, thyroid stimulating hormone (TSH), free triiodothyronine (free T3), free thyroxine (free T4), tumor markers (CEA, CA19-9).
- 8) Blood coagulation (PT, FDP, D-dimer).
- 9) Infectious diseases: HIV antigens and antibodies, HTLV-1 antibodies (if testing was performed within 3 months prior to enrollment, the data may be used with the subject's consent).
- 10) Urinalysis: specific gravity, protein, sugar, occult blood, sedimentation (white blood cells, red blood cells).
- 11) Pregnancy test (only for women of childbearing potential).
- 12) Immunological parameters.
- 13) ECG.

Test items and assessment during and after treatment

After completion of radiotherapy

(Assess the following items once within 14 days of the end date. If the test is performed on the day of the first dose of nivolumab, the same test will be used to evaluate them.)

- 1) General findings (temperature, blood pressure, pulse).
- 2) General condition: PS (ECOG).
- 3) Subjective and objective symptoms: fever, nausea, vomiting, diarrhea, decreased appetite, etc. (to be confirmed according to CTCAE v4.0 Japanese translation).
- 4) Blood count (peripheral blood): white blood cell count and fractions, red blood cell count, hemoglobin, MCV, MCH, MCHC, Ht, platelets.
- 5) Blood biochemistry: total protein, albumin, total bilirubin, direct bilirubin, AST, ALT, ALP, γ -GTP, BUN, creatinine, LDH, uric acid, CPK, P, Ca, Na, K, Cl, CRP, blood glucose.
- 6) Presence of adverse events (CTCAE v4.0 Japanese translation).
- 7) Immunological parameters.

During nivolumab administration

(After the second dose, assess the following items on the day of administration or the day before administration. Assess following items once from 7 days before to 7 days after the imaging examination date.)

- 1) General findings (temperature, blood pressure, pulse).
- 2) General condition: PS (ECOG).
- 3) Subjective and objective symptoms: fever, nausea, vomiting, diarrhea, decreased appetite, etc. (to be confirmed according to CTCAE v4.0 Japanese translation).
- 4) Blood count (peripheral blood): white blood cell count and fractions, red blood cell count, hemoglobin, MCV, MCH, MCHC, Ht, platelets.
- 5) Blood biochemistry: total protein, albumin, total bilirubin, direct bilirubin, AST, ALT, ALP, γ -GTP, BUN, creatinine, LDH, uric acid, CPK, P, Ca, Na, K, Cl, CRP, blood sugar.
(The following items are only available at the third and sixth doses) RA, ANA, SP-D, KL-6, TSH, free T3, free T4, tumor markers (CEA, CA19-9).
- 6) Contrast-enhanced CT of the chest, abdomen and pelvis (at third and sixth doses). PET-CT is also acceptable. Add MRI if necessary.
- 7) Presence or absence of PD (diagnosed comprehensively based on imaging and clinical findings).
- 8) Presence or absence of adverse events (CTCAE v4.0 Japanese translation).
- 9) Immunological parameters.

During observation

(Assess following items once from 14 days before to 14 days after the 3rd and 6th dose of Nivolumab and Day120.)

- 1) Contrast-enhanced CT of chest, abdomen and pelvis. PET-CT is also acceptable. Add MRI if necessary.

After completion of the protocol

(Assess following items once from 14 days before to 14 days after the Day180.)

- 1) General findings (temperature, blood pressure, pulse).
- 2) General condition: PS (ECOG).
- 3) Subjective and objective symptoms: fever, nausea, vomiting, diarrhea, decreased appetite, etc. (to be confirmed according to CTCAE v4.0 Japanese translation).
- 4) Blood count (peripheral blood): white blood cell count and fractions, red blood cell count, hemoglobin, MCV, MCH, MCHC, Ht, platelets.
- 5) Blood biochemistry: total protein, albumin, total bilirubin, direct bilirubin, AST, ALT, ALP, γ -GTP, BUN, creatinine, LDH, uric acid, CPK, P, Ca, Na, K, Cl, CRP, blood sugar, RA, ANA, SP-D, KL-6, TSH, free T3, free T4, tumor markers (CEA, CA19-9).

- 6) Contrast-enhanced CT of chest, abdomen and pelvis. PET-CT is also acceptable. Add MRI if necessary.
- 7) Presence or absence of PD (diagnosed comprehensively based on imaging and clinical findings).
- 8) Presence or absence of adverse events (CTCAE v4.0 Japanese translation).
- 9) Immunological parameters.

At the time of cessation of treatment

(Assess following items once within 14 days after the decision to discontinue. Assessment of following items within 14 days prior to the date of cessation of treatment is valid. If the subject is dead, hospitalized in another hospital, or otherwise unable to come to the hospital, these situations should be noted).

- 1) General findings (temperature, blood pressure, pulse).
- 2) General condition: PS (ECOG).
- 3) Subjective and objective symptoms: fever, nausea, vomiting, diarrhea, decreased appetite, etc. (to be confirmed according to CTCAE v4.0 Japanese translation).
- 4) Blood count (peripheral blood): white blood cell count and fractions, red blood cell count, hemoglobin, MCV, MCH, MCHC, Ht, platelets.
- 5) Blood biochemistry: total protein, albumin, total bilirubin, direct bilirubin, AST, ALT, ALP, γ -GTP, BUN, creatinine, LDH, uric acid, CPK, P, Ca, Na, K, Cl, CRP, blood sugar, RA, ANA, SP-D, KL-6, TSH, free T3, free T4, tumor markers (CEA, CA19-9).
- 6) Contrast-enhanced CT of chest, abdomen and pelvis. PET-CT is also acceptable. Add MRI if necessary.
- 7) Presence or absence of PD (judged comprehensively based on imaging and clinical findings).
- 8) Presence or absence of adverse events (CTCAE v4.0 Japanese translation).
- 9) Immunological parameters.

Inspection schedule

| | | | | | | | | | |
|---|---|---|---|---|---|---|---|---|---|
| Period | | | | | | | | | |
| Patient background | ○ | | | | | | | | |
| General findings | ○ | ○ | | | | | | | |
| General condition | ○ | ○ | ○ | | | | | | |
| Subjective and objective symptoms | ○ | ○ | ○ | ○ | | | | | |
| Imaging | ○ | | | | ○ | | | | |
| ECG | ○ | | | | | | | | |
| Blood count | ○ | | ○ | ○ | ○ | ○ | ○ | ○ | ○ |
| Coagulation | ○ | | | | | | | | |
| Blood biochemistry | ○ | | ○ | ○ | ○ | ○ | ○ | ○ | ○ |
| Urinalysis | ○ | | | | | | | | |
| Infection | ○ | | | | | | | | |
| Pregnancy test (if required)) | | ○ | | | | | | | |
| Immunological parameters① ^{#1} | | ○ | | | | | | | |
| Immunological parameters② ^{#2} | ○ | | ○ | | ○ | | | | ○ |

#1 Histological examination

#2 Peripheral blood test

The volume of blood required for immunological parameters is 30 mL each time.

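### Patients who stop for clinical progression without the qualifying scans can fall out of the primary disease control rate, which then reads too high

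*Protocol*

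**What the plan says.** **Endpoint definition (Protocol 2.6, primary endpoint).** Response is read on CT, MRI or PET-CT, with "progressive disease (PD) at each imaging time according to the RECIST Guidelines Version 1.1". The lesions that count are limited: "target lesions other than those treated with local radiotherapy are considered as target lesions". A patient without confirmed CR or PR is given stable disease on this condition: "the patient has no PD on the 6th dose of nivolumab and Day 120, the best overall response is considered to be SD". Two sentences deal with gaps: "If imaging is not available, the patient is considered deficient (NE" and "If the lesions cannot be evaluated based on the above criteria, they will not be included in the analysis for best overall response".

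**Data collection (Protocol 2.7).** During nivolumab the list includes "Presence or absence of PD (diagnosed comprehensively based on imaging and clinical findings". The item recurs at Day 180 and, at cessation of treatment, as "Presence or absence of PD (judged comprehensively based on imaging and clinical findings". For Day 120 only imaging is listed. The section does not say what the item is for, and does not restrict it to non-irradiated lesions.

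**Stopping and follow-up scans.** Section 2.5 lists worsening symptoms from disease progression among the reasons to stop nivolumab, with no imaging criterion attached. It asks for a discontinuation examination if circumstances allow. The cessation list in 2.7 includes CT but provides for patients who have died or cannot attend.

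**Analysis.** Protocol 2.10 analyses the FAS and defines the rate as patients with CR, PR or SD over the number of eligible patients. SAP 6.1 repeats the response table and the exact 90% interval, but names no denominator and no treatment of non-evaluable patients. SAP 6.5 plans no sensitivity analysis for missing values.

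**The concern.** The protocol collects two records of progression and links only one of them to the endpoint. That would be a matter of tidiness if every patient had the scans that 2.6 needs. A patient who deteriorates and stops before the sixth dose will often not have them. The team has then recorded progression in the 2.7 item, yet the endpoint rule has no category for the patient.

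These patients are very probably treatment failures. If they are left out, the primary rate is computed on those well enough to reach the later scans. In an open single-arm study with no comparator, that bias goes straight into the headline figure. Because the documents point both to exclusion and to inclusion, the choice could also be made after the data are seen.

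**Working it through.** **Step 1. Follow one patient through the text.** Nivolumab starts on Day 15 to 22 and is given every two weeks, so with no delay the sixth dose falls on Day 15 + 70 = 85 to Day 22 + 70 = 92. Suppose the patient stops after the fourth dose for clinical worsening, and no later scan is obtained.

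- CR or PR: needs consecutive responses, which are not present.
- SD: needs no progression at the sixth dose and at Day 120. The sixth dose was not given and the Day 120 scan was not done.
- PD: needs a RECIST read showing it. There is none.

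A cessation scan without RECIST progression would not change this, because the SD condition is still unmet. The three sections then treat the patient as follows:

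| Place | Status of this patient |
|---|---|
| Protocol 2.7, cessation item | Progressed |
| Protocol 2.6 | Non-evaluable and left out of best overall response |
| Protocol 2.10 | In the denominator if eligible, not in the numerator |
| SAP 6.1 | Not addressed |

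**Step 2. The plan's own figure.** Section 2.8 sets 40%, an improvement of 20 points (read as 60%), one-sided 5% and power 80%, and gives 39 cases. The formula is not named. The arcsine formula reproduces it:

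n = [(z0.95 + z0.80) / (2 arcsin √0.60 − 2 arcsin √0.40)]² = 38.12, rounded up to 39.

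The planned number is 40. The one-sided 5% level corresponds to the lower limit of the two-sided 90% interval in 2.10 and SAP 6.1, and 40% is the reference rate. No document states that the limit must exceed 40%. That comparison is my inference.

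**Step 3. Effect of leaving patients out.** If k of N patients are dropped and none was in the numerator, the rate is multiplied by N/(N − k). The direction is therefore fixed: it can only go up. The exact lower limit L solves P(X ≥ x | n, L) = 0.05, that is, the 5% quantile of Beta(x, n − x + 1).

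Take 21 controlled patients among 40 eligible and treated. The documents give no number for k, so a range is shown.

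| Left out | Rate | 90% lower limit |
|---|---|---|
| 0 | 21/40 = 52.5% | 38.5% |
| 1 | 21/39 = 53.8% | 39.6% |
| 2 | 21/38 = 55.3% | 40.7% |
| 3 | 21/37 = 56.8% | 42.0% |

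With all 40 in the denominator, 22 controlled patients are needed for the limit to pass 40% (22/40: 40.9%). With two dropped, 21 are enough.

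**The case against.** Five things can be said for the plan.

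1. **RECIST governs.** Section 2.6 names RECIST 1.1 in the same paragraph as the SD rule, and 2.7 is a list of observations. Section 2.10 and SAP 6.1 summarise responses of target lesions, and the efficacy listing in SAP 8.7 holds best overall response and tumour diameters, with no field for the comprehensive item. This stands in full.
2. **Section 2.10 already gives the conservative answer.** If its denominator is followed, these patients count as not controlled. This stands as far as it goes, but 2.6 points the other way, and the SAP, which should settle it, is silent.
3. **Scans are scheduled** at the third and sixth doses, Day 120, Day 180 and cessation, so some of these patients will have RECIST progression on film. True. It lowers the number affected but does not say how to count the rest.
4. **The exclusion sentence has lesions, not patients, as its subject.** That is fair, but a patient whose lesions cannot be evaluated has no best overall response under either reading.
5. **One missing patient always matters near a boundary.** Also fair. The 21-patient example shows scale and is not a forecast.

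A reader might infer more: that one patient can be stable under 2.6 and progressed under 2.7 within the endpoint, or that clinical opinion could cancel RECIST growth, with a calculable loss of power or rise in type I error. The documents do not support this. No passage feeds the 2.7 item into best overall response or lets it override a scan, and no rate of disagreement is given from which such figures could be computed.

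**Conclusion.** The point holds as a gap in how clinical progression without qualifying scans is counted, not as a contradiction in how progression is defined. Sections 2.6 and 2.10 give different denominators for the same patients, and following 2.6 removes likely failures and inflates the disease control rate.

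In the illustration, dropping 2 of 40 adds 2.8 points (52.5% to 55.3%) and moves the lower limit from 38.5% to 40.7%. This assumes that 40 patients are eligible and treated, that 21 are controlled, and that none of those dropped had a confirmed response. The number dropped is an assumption, and reading the limit against 40% is an inference. The direction of the bias depends on neither. It should be corrected before the data are fixed.

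**What to change.** In Protocol 2.6 and 2.10 and in SAP 6.1:

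- State that progression, and its absence in the SD rule, mean the RECIST 1.1 read of the relevant lesions. For the primary endpoint these are the non-irradiated ones.
- State that patients who stop for clinical progression without the scans needed for a response category stay in the denominator and count as not controlled. Bring the exclusion sentence in 2.6 into line with the denominator in 2.10.

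In Protocol 2.7, state the purpose of the comprehensive progression item and whether it has any role in the endpoint.

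In the SAP, add a table of discordant RECIST and comprehensive calls at the visits where both are recorded. Day 120 cannot be included, because only imaging is listed there.

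The cost is a few sentences and one table from data already planned. The reported rate may be slightly lower than under exclusion.
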